8. STUDY POPULATION

8.1. Number of Subjects

A total of approximately 200 subjects with previously untreated IDH1m AML will participate in this study.

8.2. Inclusion Criteria

Subjects must meet all of the following criteria to be eligible for inclusion in the study:

1. Be ≥ 18 years of age and meet at least 1 of the following criteria defining ineligibility for intensive IC:
 - a. ≥ 75 years old
 - b. ECOG PS = 2
 - c. Severe cardiac disorder (eg, congestive heart failure requiring treatment, LVEF $\leq 50\%$, or chronic stable angina)
 - d. Severe pulmonary disorder (eg, diffusing capacity of the lungs for carbon monoxide $\leq 65\%$ or forced expiratory volume in 1 second $\leq 65\%$)
 - e. Creatinine clearance < 45 mL/minute
 - f. Bilirubin > 1.5 times the upper limit of normal (\times ULN)
 - g. Any other comorbidity that the Investigator judges to be incompatible with intensive IC must be reviewed and approved by the Medical Monitor before study enrollment.
2. Have previously untreated AML, defined according to WHO criteria. Subjects with extramedullary disease alone (ie, no detectable bone marrow and no detectable peripheral blood AML) are not eligible for the study.
3. Have an IDH1 mutation resulting in an R132C, R132G, R132H, R132L, or R132S substitution, as determined by central laboratory testing (using an investigational polymerase chain reaction [PCR] assay, Abbott RealTime IDH1) in their bone marrow aspirate (or peripheral blood sample if bone marrow aspirate is not available, with Medical Monitor approval).

(Note: Local testing for eligibility and randomization is permitted with Medical Monitor approval; however, results must state an IDH1 mutation resulting in an R132C, R132G, R132H, R132L, or R132S substitution. Bone marrow aspirate [or peripheral blood sample if bone marrow aspirate is not available, with Medical Monitor approval] for central laboratory testing must have been sent with proof of shipment to the central laboratory prior to randomization.)
4. Have an ECOG PS score of 0 to 2.
5. Have adequate hepatic function, as evidenced by:
 - a. Serum total bilirubin $\leq 2 \times$ ULN, unless considered to be due to Gilbert's disease or underlying leukemia, where it must be $< 3 \times$ ULN.
 - b. Aspartate aminotransferase (AST), alanine aminotransferase (ALT), and alkaline phosphatase (ALP) $\leq 3.0 \times$ ULN, unless considered to be due to underlying leukemia.

6. Have adequate renal function, as evidenced by serum creatinine $\leq 2.0 \times$ ULN or creatinine clearance > 30 mL/min based on the Cockcroft-Gault glomerular filtration rate.
7. Have agreed to undergo serial blood and bone marrow sampling.
8. Be able to understand and willing to sign an informed consent form (ICF).
9. Be willing to complete QoL assessments during study treatment and at the designated time points following treatment discontinuation.
10. If female with reproductive potential, must have a negative serum pregnancy test prior to the start of study therapy. Female subjects with reproductive potential are defined as sexually mature women who have not undergone a hysterectomy, bilateral oophorectomy, or tubal occlusion or who have not been naturally postmenopausal for at least 24 consecutive months. Females of reproductive potential, as well as fertile men with female partners of reproductive potential, must use 2 effective forms of contraception (including at least 1 barrier form) from the time of giving informed consent throughout the study and for 90 days (both females and males) following the last dose of study drug(s). Effective forms of contraception are defined as hormonal oral contraceptives, injectables, patches, intrauterine devices, intrauterine hormone-releasing systems, bilateral tubal ligation, condoms with spermicide, or male partner sterilization. Coadministration of AG-120 may decrease the concentrations of hormonal contraceptives (Section 9.13.2).

8.3. Exclusion Criteria

Subjects who meet any of the following criteria will be excluded from the study:

1. Are candidates for intensive IC for their AML.
2. Have received any prior treatment for AML with the exception of noncolytic treatments to stabilize disease such as hydroxyurea or leukapheresis.
3. Have received a hypomethylating agent for myelodysplastic syndrome (MDS).
4. Subjects who had previously received treatment for an antecedent hematologic disorder, including investigational agents, may not be randomized until a washout period of at least 5 half-lives of the investigational agent has elapsed since the last dose of that agent.
5. Have received prior treatment with an IDH1 inhibitor.
6. Have a known hypersensitivity to any of the components of AG-120, matched placebo, or azacitidine.
7. Are female and pregnant or breastfeeding.
8. Are taking known strong CYP3A4 inducers or sensitive CYP3A4 substrate medications with a narrow therapeutic window, unless they can be transferred to other medications within ≥ 5 half-lives prior to dosing (Appendix 15.6).
9. Exclusion Criterion #9 was removed in Protocol Amendment 5, Version 6.0.
10. Have an active, uncontrolled, systemic fungal, bacterial, or viral infection without improvement despite appropriate antibiotics, antiviral therapy, and/or other treatment.

11. Have a prior history of malignancy other than MDS or myeloproliferative disorder, unless the subject has been free of the disease for ≥ 1 year prior to the start of study treatment. However, subjects with the following history/concurrent conditions or similar indolent cancer are allowed to participate in the study:
 - a. Basal or squamous cell carcinoma of the skin
 - b. Carcinoma in situ of the cervix
 - c. Carcinoma in situ of the breast
 - d. Incidental histologic finding of prostate cancer
12. Have had significant active cardiac disease within 6 months prior to the start of study treatment, including New York Heart Association Class (NYHA) Class III or IV congestive heart failure (see Appendix 15.2), myocardial infarction, unstable angina, and/or stroke.
13. Have a heart-rate corrected QT interval using Fridericia's method (QTcF) ≥ 470 msec or any other factor that increases the risk of QT prolongation or arrhythmic events (eg, NYHA Class III or IV congestive heart failure, hypokalemia, family history of long QT interval syndrome). Subjects with prolonged QTcF interval in the setting of bundle branch block may participate in the study.
14. Have a known infection caused by human immunodeficiency virus (HIV) or active hepatitis B virus (HBV) or hepatitis C virus that cannot be controlled by treatment.
15. Have dysphagia, short-gut syndrome, gastroparesis, or any other condition that limits the ingestion or gastrointestinal absorption of orally administered drugs.
16. Have uncontrolled hypertension (systolic blood pressure [BP] > 180 mmHg or diastolic BP > 100 mmHg).
17. Have clinical symptoms suggestive of active central nervous system (CNS) leukemia or known CNS leukemia. Evaluation of cerebrospinal fluid during Screening is only required if there is a clinical suspicion of CNS involvement by leukemia during Screening.
18. Have immediate, life-threatening, severe complications of leukemia, such as uncontrolled bleeding, pneumonia with hypoxia or sepsis, and/or disseminated intravascular coagulation.
19. Have any other medical or psychological condition deemed by the Investigator to be likely to interfere with the subject's ability to give informed consent or participate in the study.
20. Are taking medications that are known to prolong the QT interval (Appendix 15.5) unless they can be transferred to other medications within ≥ 5 half-lives prior to dosing, or unless the medications can be properly monitored during the study. (If equivalent medication is not available, heart rate corrected QT interval [QTc] will be closely monitored as defined in Section 9.13.2).
21. Subjects with a known medical history of progressive multifocal leukoencephalopathy (PML).

8.4. Subject Identification and Registration

Subjects who are candidates for enrollment into the study will be evaluated for eligibility by the Investigator to ensure that the inclusion and exclusion criteria (see Sections 8.2 and 8.3, respectively) have been satisfied and that the subject is eligible for participation in this clinical study. The Medical Monitor will confirm eligibility for all subjects prior to receipt of the first dose of AG-120 or placebo.

8.5. Subject Withdrawal Criteria

Subjects have the right to withdraw from the study at any time for any reason. A subject's withdrawal from treatment or the study will not jeopardize the relationship with their healthcare providers or affect their future care. Subjects may choose to withdraw from the study treatment but agree to remain on study for follow-up contact. This decision must be recorded in writing by the study site.

Should a subject decide to withdraw, all efforts will be made to complete and report the protocol-defined study observations as completely as possible and to determine the reason for withdrawal.

In the event a subject is withdrawn from study treatment or from the study, the Medical Monitor must be informed. If there is a medical reason for withdrawal, the subject will remain under the supervision of the Investigator until satisfactory health has returned.

When a subject discontinues study treatment or withdraws from the study, the primary reason for discontinuation or withdrawal must be recorded in the appropriate Section of the electronic case report form (eCRF) and all efforts will be made to complete and report final study observations as thoroughly as possible.

8.5.1. Withdrawal from Study Treatment

Subjects may withdraw or be withdrawn from study treatment for any of the following reasons:

- Withdrawal by subject
- AE
- Death
- Relapse/disease progression
- Treatment failure (subjects with a response less than CR after receiving treatment for at least 24 weeks)
- Clinical progression (within 24 weeks) not confirmed by IWG assessment
- Subject lost to follow-up
- Confirmed pregnancy for female subjects only (study therapy should be immediately interrupted based upon a positive urinary human chorionic gonadotropin [hCG] test, and permanently discontinued if confirmed by a serum beta-human chorionic gonadotropin [β -hCG] test)
- Protocol violation: non-adherence to study treatment regimen or protocol requirements

The Investigator should follow each AE until the event has resolved to baseline grade or better, the event is assessed as stable by the Investigator, the subject is lost to follow-up, or the subject withdraws consent. If a subject withdrew from treatment because of an AE, every effort must be made to perform protocol-specified safety follow-up procedures (see Section 10.6).

8.5.2. Event-Free Survival Follow-up

All subjects who discontinue study treatment without experiencing any 1 of the following: death, disease relapse, treatment failure, or withdrawal of consent, will be followed every Day 1 (± 7 days) of Weeks 9, 17, 25, 33, 41, 53, and every 24 weeks thereafter for EFS until they experience treatment failure, relapse, death, withdraw from the study, or until the time when 173 EFS events have occurred or as deemed necessary by the IDMC.

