6.2.1. Primary Endpoint

The primary endpoint of the study is EFS, which is defined as the time from randomization until treatment failure, relapse from remission, or death from any cause, whichever occurs first. Treatment failure is defined as failure to achieve CR by Week 24.

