8.5.4. Withdrawal from the Study

Subjects discontinuing study treatment prior to experiencing disease progression/relapse will continue to be followed for disease progression/relapse/death. The reasons for withdrawal from the study include:

- Withdrawal by subject
- Subject lost to follow-up
- Study terminated by Sponsor
- Death

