9.8. Criteria for Dose Escalation, Dose Modification, or Discontinuation of Study Drug

9.8.1. AG-120/Placebo Dose Modification and Stopping Criteria

Intra-subject dose escalation will not be permitted.

For any AE, including AEs not specifically mentioned in Table 1, the Investigator may decide to delay dosing or modify the dose of AG-120/placebo based on clinical judgment. All dose modifications of AG-120/placebo should be discussed with the Sponsor prior to implementation. Dose modifications of AG-120/placebo from 500 mg to 250 mg will be permitted on study for management of AEs (see Table 1). If more than 1 AE occurs that would require a dose modification, upon resolution of all AEs to baseline or Grade 1, AG-120/placebo should be dose-reduced to 250 mg. Subjects who have had their dose of AG-120/placebo reduced due to a Grade ≥ 3 AE will be permitted to re-escalate to 500 mg after discussion with the Sponsor's Medical Monitor.

Dose delays for reasons other than management of AEs are discouraged. Dose delays up to 28 days will be permitted at the discretion of the Investigator in consultation with the Medical Monitor for reasons including management of AEs and for mitigating circumstances (eg, planned procedures).

Azacitidine and AG120/placebo can be interrupted concurrently, or either agent alone, depending on the attribution to an AE by the Investigator. If azacitidine is permanently discontinued, treatment with AG-120/placebo may continue at the discretion of the Investigator and with the agreement of the Medical Monitor, provided that the subject is in CR or CRi (including CRp).

If a subject cannot resume AG-120/placebo within 28 days, the subject should be discontinued from study treatment if they have previously discontinued treatment with azacitidine. Other reasons for treatment termination are provided in Section 8.5. If AG-120 or placebo is discontinued, the subject will complete the EOT and Follow-up Visits, and will then enter EFS Follow-up (if the subject has not already experienced an EFS event [eg, treatment failure, relapse, or death]) and subsequent Survival Follow-up. If a dose is delayed, visit days (in cycles/days) will be paused until the next planned study visit (eg, if a dose is held on C3D1, the next scheduled visit when dosing begins again will become C3D1); disease response assessments should continue regardless of dose delays.

Table 1: Management of Adverse Events

Adverse Events (AEs)	Action

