10.8. Efficacy Assessments

10.8.1. Response to Treatment

The efficacy of AG-120 will be evaluated by Investigator-assessed response to treatment based on modified IWG Response Criteria for AML and ELN guidelines, including assessment of the following (see Table 10):

- EFS is defined as the time from randomization until treatment failure, relapse from remission, or death from any cause, whichever occurs first. Treatment failure is defined as failure to achieve CR by Week 24. Subjects who do not achieve CR by Week 24 will be considered to have had an event at Day 1 of randomization. For the remaining CR responders, the event time will be the time of either disease relapse or death, whichever occurs first.
- CR is defined as bone marrow blasts <5% and no Auer rods; absence of extramedullary disease; ANC $\geq 1.0 \times 10^9/L$ (1000/ μ L); platelet count $\geq 100 \times 10^9/L$ (100,000/ μ L); and independence of red blood cell transfusions.

- CRh is defined as a CR with partial recovery of peripheral blood counts (< 5% bone marrow blasts, platelets >50,000/ μ L, and ANC >500/ μ L). CRh will be derived by the Sponsor.
- ORR is defined as the rate of CR, CRi (including CRp), PR, and MLFS. The best response is calculated using the following order: 1) CR; 2) CRi (including CRp); 3) PR, and 4) MLFS.

Disease response to treatment will be assessed through the evaluation of bone marrow biopsies and/or aspirates, along with complete blood counts and examination of peripheral blood films.

Treatment decisions will be based on Investigator's assessment.

Subjects will have the extent of their disease assessed and recorded: at Screening (or as part of the Pre-screening process, as long as it is within 28 days prior to randomization); Day 1 (\pm 7 days) of Weeks 9, 17, 25, 33, 41, 53, and every 24 weeks thereafter; at EOT; as dictated by physical exam and/or blood counts; and/or any time that disease progression is suspected. For subjects who discontinue treatment prior to disease progression, disease assessments will be performed on the same schedule until disease progression/relapse.

Subjects will also be evaluated for their RBC and platelet transfusion requirements, including dates of the transfusion(s) and number of units administered, at each disease response assessment.

The criteria outlined in [Table 10](#) and [Table 11](#) will be used to assess response to treatment.

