- If the event date is prior to day 1 of week 53 (relative day since randomization $\leq 52 \times 7 = 364$), and the difference of event date and the last adequate disease assessment $> (8 \times 2 + 1) \times 7 = 119$, then the event is considered as occurring after two or more missing disease assessments
- If the event date is between day 1 of week 53 and day 1 of week 77 (relative day since randomization > 364 and ≤ 532) and the difference of event date and the last adequate disease assessment $> (8 + 12 + 1) \times 7 = 147$, then the event is considered as occurring after two or more missing disease assessments
- If the event date is between day 1 of week 77 and day 1 of week 101 (relative day since randomization > 532 and ≤ 700) and the difference event date and the last adequate disease assessment is $> (12 + 24 + 1) \times 7 = 259$, then the event is considered as occurring after two or more missing disease assessments
- If the event date is after day 1 of week 101 (relative day since randomization > 700) and the difference of event date and the last adequate disease assessment is

$>(24+24+1)\times 7=343$, then the event is considered as occurring after two or more missing disease assessments

The outcome (event or censor), type of event and the date of event or censoring to be considered for the primary analysis of EFS are presented in Table 5.

Table 5: Outcome and Event or Censoring Dates for EFS

Scenario	Date of event/censoring	Event (event type)/ Censored
CR by 24 weeks ^a then relapse	Date of relapse	Event (relapse)
CR by 24 weeks ^a then death (no relapse)	Date of death	Event (death)
CR by 24 weeks ^a then start subsequent anticancer therapy (prior to relapse or no relapse)	Date of the last adequate disease assessment documenting no relapse prior to start of subsequent anticancer therapy or missed response assessments	Censored
CR by 24 weeks ^a then relapse or death after two or more missing or inadequate disease assessments		Censored
CR by 24 weeks ^a and neither relapse nor death		Censored
On treatment ≥ 24 weeks without CR by 24 weeks ^a	Date of randomization	Event (TF, on treatment ≥ 24 weeks without CR)
Treatment discontinuation prior to 24 weeks, without CR by 24 weeks ^a		Event (TF, treatment discontinuation prior to 24 weeks without CR)

Abbreviations: CR = complete response; EFS = event-free survival; TF = treatment failure.

^a Based on the protocol schedule of assessments, "+1 week window" is allowed.

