7.7.3.2. DOCR, DOCRh, DOR, and DOCRi

DOCR is defined, for subjects who achieved CR, as the time from the first occurrence of CR to confirmed relapse or death due to any cause.

$$\text{DOCR (months)} = (\text{date of event or censoring} - \text{first date of CR} + 1) / 30.4375$$

DOCRh is defined, for subjects who achieved CR or CRh, as the time from the first occurrence of CR or CRh to confirmed relapse or death due to any cause.

$$\text{DOCRh (months)} = (\text{date of event or censoring} - \text{first date of CRh} + 1) / 30.4375$$

DOR is defined, for subjects who achieved CR, CRi (including CRp), PR, or MLFS, as the time from the first response to confirmed relapse, disease progression, or death due to any cause.

$$\text{DOR (months)} = (\text{date of event or censoring} - \text{first date of response} + 1) / 30.4375$$

DOCRi is defined, for subjects who achieved CR or CRi (including CRp), as the time from the first occurrence of CR or CRi (including CRp) to confirmed relapse or death due to any cause.

$$\text{DOCRi (months)} = (\text{date of event or censoring} - \text{first date of CR or CRi} + 1) / 30.4375$$

The outcome (event or censor), type of event and the date of event or censoring to be considered for the analysis of DOCR, DOCRh, DOR, and DOCRI are presented in [Table 8](#).

Table 8: Outcome and Event or Censoring Dates for DOCR, DOCRh, DOR, and DOCRI

Scenario	Date of event/censoring	Event (event type)/ Censored
Relapse/progression ^a	Date of relapse/progression	Event (relapse/progression)
Death (no relapse/progression)	Date of death	Event (death)
Start subsequent anticancer therapy (prior to relapse/progression or no relapse/progression)	Date of the last adequate disease assessment documenting no relapse/progression prior to start of subsequent anticancer therapy or missed disease assessments	Censored
Relapse/progression or death after two or more missing or inadequate disease assessments		Censored
Neither relapse/progression nor death		Censored

^aProgression only applies to the calculation of DOR, for which subjects with a BOR of PR may experience disease progression afterwards.

Frequency of subject with each event type and censoring reasons will be presented by treatment arm. Reasons for censoring will be summarized according to the categories in [Table 9](#) following the hierarchy shown.

Table 9: Censoring Reasons and Hierarchy for DOCR, DOCRh, DOR, and DOCRI

Hierarchy	Condition	Censoring Reason

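### The protocol contradicts itself on whether responders without CR by Week 24 keep having disease assessments after they stop treatment, which puts the response-duration endpoints at risk of informative censoring

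*Protocol*

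**What the plan says.** The entry rule for EFS Follow-up in Protocol Section 8.5.2 reads: "All subjects who discontinue study treatment without experiencing any 1 of the following: death, disease relapse, treatment failure, or withdrawal of consent, will be followed". It is repeated in the synopsis, Sections 7.1, 9.11.1 and 10.1, and Table 6 footnote 4. Section 6.2.1 fixes the key term: "Treatment failure is defined as failure to achieve CR by Week 24". Section 9.8.1 applies the same rule when AG-120 or placebo is discontinued, sending a subject to EFS Follow-up only "if the subject has not already experienced an EFS event [eg, treatment failure, relapse, or death". After the EOT visit, Table 6 places marrow, peripheral blood and response evaluation only in the EFS Follow-up column. Under Section 8.5.3, subjects alive after an EFS event are contacted every 8 weeks for survival.

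Two other current sections say something different, and neither excludes treatment failures. Section 8.5.4: "Subjects discontinuing study treatment prior to experiencing disease progression/relapse will continue to be followed for disease progression/relapse/death". Section 10.8.1: "For subjects who discontinue treatment prior to disease progression, disease assessments will be performed on the same schedule until disease progression/relapse". The marrow-sampling text in Section 10.7 and Table 6 footnote 12 also assumes that samples are taken after an EFS event.

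Section 6.1.2 lists a comparison of DOCR, DOCRh, DOR and DOCRi among the additional secondary objectives. SAP Section 7.7.3.2 measures each from first response to confirmed relapse (or progression, for DOR) or death. SAP Table 8 censors one further case at the last adequate assessment: "Relapse/progression or death after two or more missing or inadequate disease assessments".

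**The concern.** For EFS, anyone without CR by Week 24 is a treatment failure. For the duration endpoints, many of the same people are responders whose relapse date is the outcome. The protocol expects such people: Sections 7.1 and 9.11.1 let a subject below CR at 24 weeks stay on treatment if there is defined benefit. If that subject later stops treatment while still in response, Section 8.5.2 ends disease assessment and Section 10.8.1 continues it.

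Two sites could therefore each comply with the protocol and collect different data. Where assessment ends, relapse goes unseen and the subject is censored at the last assessment. Subjects who stop treatment while below CR are unlikely to have the same relapse risk as those who stay on, so the censoring may be informative and would tend to lengthen the Kaplan-Meier estimates. A death that comes long enough after the last assessment is also censored rather than counted.

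**Working it through.** **1. Trace one subject under each rule.** Take a subject in CRi from Week 17 who stays on treatment under the benefit rule and stops for toxicity at the Week 41 visit, still in CRi, with the EOT assessment done at that visit.

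| Question | 8.5.2, 9.8.1, Table 6 | 8.5.4, 10.8.1 |
|---|---|---|
| EFS status | Treatment failure (no CR by Week 24) | Same |
| Enters EFS Follow-up? | No | Not made a condition |
| Scheduled assessments after Week 41 | None | Weeks 53, 77 and on, until progression/relapse |
| Relapse at Week 50 | Not observed on schedule | Observable at Week 53 |

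A responder below CR who stops before Week 24 meets the same conflict later. Section 8.5.2 would follow that subject until treatment failure is established, and SAP Table 5 (row "Treatment discontinuation prior to 24 weeks, without CR by 24 weeks") then dates the failure at randomization.

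**2. Which deaths are censored.** SAP Section 7.7.3.2 gives no windows for counting missed assessments. The only ones stated are those for EFS in SAP Section 7.7.1.1.1: 119 days for events up to day 364, 147 up to day 532, 259 up to day 700, and 343 after that. Assuming they apply here, with the last assessment at day 40 × 7 = 280:

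- Death by day 364: the gap is at most 364 − 280 = 84, not above 119, so it counts.
- Death on days 365 to 427: the gap is at most 427 − 280 = 147, so it counts.
- Death on days 428 to 532: the gap exceeds 147, so it is censored.
- Death on days 533 to 539: the gap is at most 539 − 280 = 259, so it counts.
- Death after day 539: censored, since the gap exceeds 259 up to day 700 and is above 420 (over 343) after that.

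Deaths in the first 147 days (21 weeks) after the last assessment therefore count. Most later ones do not.

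**3. Size of the group.** The rates come from Protocol Section 12.13.2 (Table 13): CR 20% vs 40%, CR + CRh 25% vs 45%, ORR 32% vs 52%, with 100 per arm.

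The stated powers reproduce. With power = Φ{[(p2 − p1)√n − 1.96√(2p̄(1 − p̄))] / √[p1(1 − p1) + p2(1 − p2)]} and n = 100, the results are 87.6%, 84.8% and 82.2%, against 86%, 84% and 81% in the plan. No design figure is in dispute. The rates are used only to size the group.

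- Responders without CR, control: 32 − 20 = 12, and 12/32 = 38%.
- Responders without CR, AG-120: 52 − 40 = 12, and 12/52 = 23%.
- Both arms: 24 of 84 responders, 29%.
- CRh without CR, control: 25 − 20 = 5, and 5/25 = 20%.
- CRh without CR, AG-120: 45 − 40 = 5, and 5/45 = 11%.

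Only those who stop treatment before relapse or progression are affected, so these are ceilings for responders who never reach CR. The plan uses 20% and 40% both for CR by 24 weeks and for CR at any time, so the number of late CRs, who are also affected, cannot be derived.

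**The case against.** The strongest reply is that the protocol already requires the missing follow-up. Sections 8.5.4 and 10.8.1 are current text and cover these subjects, and the marrow footnote points the same way. A reader might infer from Section 8.5.2 that these responders are barred from assessment and that the duration objectives cannot be answered. The documents do not support that: they state both rules. This part of the reply stands, and the finding is a contradiction, not an absence. It does not remove the problem, because the schedule table and every copy of the entry rule point one way and two sentences point the other.

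A reader might also take 38% and 23% as the share of responders lost. They are not, since subjects below CR may remain on treatment with scheduled assessments, and the documents give no rate of stopping before relapse.

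Nor do the documents support saying that all later deaths are censored. Deaths are still collected in survival follow-up, and those inside the missed-assessment window count.

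Finally, the endpoints are of modest rank. They are additional secondary endpoints with no alpha control (Protocol Section 12.5), and the SAP plans Kaplan-Meier summaries by arm with no between-arm test. This limits the weight of the point but leaves the inconsistency in place.

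**Conclusion.** The concern holds as an internal contradiction that should be resolved. For responders without CR by Week 24 who stop treatment before relapse or progression, the protocol both ends and continues disease assessment. Where it ends, relapse is unobserved and deaths beyond the missed-assessment window are censored, with a risk that DOR, DOCRi, DOCRh and late-CR DOCR are overstated.

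The affected number cannot be calculated from the documents. Its ceiling at planning rates, leaving aside late CRs, is 12 responders per 100 subjects in each arm. The ceiling is a larger fraction of responders in control, but this does not show a larger bias there. An illustration makes the point. Assume exponential durations with medians of 14.6 and 19.2 months for CR responders (the plan's EFS medians, measured from randomization and used only as stand-ins). Assume 4 to 8 months for the others, of whom 25% to 50% are censored before relapse. The Kaplan-Meier median DOR then rises by roughly 0.3 to 3 months in control and 0.5 to 3 months in AG-120, depending mainly on how stopping relates to relapse. The shift in months is not consistently larger in either arm. These inputs are assumptions, and no estimate of bias should be taken from them.

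Primary EFS is unaffected because these subjects already have an event at randomization. The key secondary tests do not use response duration.

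**What to change.** Reconcile the passages so that Section 8.5.2, its copies (synopsis, Sections 7.1, 9.11.1 and 10.1, Table 6 footnote 4), Section 9.8.1 and the Table 6 columns agree with Sections 8.5.4 and 10.8.1. State that a subject with an ongoing CR, CRh, CRi/CRp, PR or MLFS at discontinuation stays on the disease-assessment schedule until relapse, progression, death or unblinding, even if treatment failure for EFS has been recorded.

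As a fallback, for subjects whose assessments have already stopped under Section 8.5.2, add a line to SAP Table 8 that the missed-assessment rule does not censor a later death, at least as a sensitivity analysis. Say also which missed-assessment windows apply to the duration endpoints. Once assessments continue for everyone in response, the fallback has little left to act on.

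The cost is a wording amendment, a note to sites and one or two SAP lines. The continued marrow and blood assessments in off-treatment responders are a real burden, but Section 10.8.1 already requires them.
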